3.2. Discussion of study design, including the choice of control groups

This is a randomized, double-blind, placebo-controlled, Phase 2, proof of concept study in hospitalized patients with mild to moderate pneumonia due to COVID-19 infection. The rationale for this study is outlined in [Section 1.1](#) and described in detail below.

The study is designed to obtain initial safety, efficacy, tolerability, and PK of antroquinonol in patients in a sentinel cohort. Once the DMC assesses safety, efficacy, tolerability, and PK of a sentinel cohort, patient enrollment will resume. The study will assess the efficacy and safety in all of the patients (174 patients).

Antroquinonol has been studied for NSCLC and pancreatic cancer. Preclinical studies showed that antroquinonol appeared to distribute to the lungs more than any other organ, followed by heart, kidneys, and small intestine ([Section 5.2.3 of the IB⁵](#)). Hence, the sponsor has planned use to assess the safety and efficacy of antroquinonol in the COVID-19 patient population.

The variability of individual clinical courses in COVID-19 and the incomplete understanding of this newly recognized disease can seriously affect the reliability of any conclusions based on uncontrolled data. Therefore, per the FDA's recommendation, this is a randomized, placebo-controlled study.

There are safety concerns in this patient population, both because of risks associated with the disease and because of the potential for adverse effects from the treatment that might be difficult to recognize.

In addition, altering the immune response during an acute infection could theoretically have either beneficial or harmful consequences that cannot be precisely predicted. For this reason, the DMC will review safety data in 2 interim analyses, and will continuously monitor for safety until completion.

The safety endpoints in this study are standard. Assessment of AEs, vital signs, complete physical examination, 12-lead ECGs, chest imaging, and safety laboratory tests are planned to be conducted and provide a robust approach to assess the safety of this patient population.

Efficacy endpoints have been chosen to assess virological and clinical parameters to evaluate clinical improvement including measures that maximize objectivity such as, requirement of ICU care, and vital status, and also include the WHO COVID-19 Clinical Improvement Ordinal Scale.

The PK of antroquinonol will be assessed from blood samples taken after the first study drug dose of the day on Day 3 and Day 14 (if patients are still hospitalized), in the sentinel cohort. Although PK has been well characterized in earlier studies, this is an acute patient population which may experience third-spacing and may be hemodynamically unstable. For this reason, intensive serial plasma PK samples (7-8 samples per patient) are being collected on Day 3 from hospitalized patients to characterize the PK of antroquinonol in the COVID-19 patient population. Every effort will be made to have PK samples taken close to the times as other blood sampling for serum to reduce the number of contacts between hospital staff and the patient. The PK samples will not be collected for the expansion cohort.

3.3. End of study definition

The end of the study is defined as the date of the last visit of the last patient in the study.

3.4. Selection of doses in the study

Antroquinonol is already in clinical development, albeit in cancer patients, and shown to be well tolerated. Levels have included oral single doses of 50-600 mg and 200 mg BID (BID use has occurred due to a short plasma half-life of 1.30 to 4.33 hours). For the proposed clinical work, a starting dose of 100mg (given BID due to short half-life) is proposed based around anti-inflammatory activity in mouse efficacy work and the rat no-observed-adverse-effect-level (NOAEL) from toxicology testing. In the former, a 15-50 mg/kg/12.3 body surface factor was calculated to correspond to a 1.22-4.07 mg/kg human equivalent dose, or 85-285 mg for a 70 kg person. Therefore, a dose of 100 mg BID is within the animal efficacy range. The proposed dose is also supported by the rat study NOAEL on a mg/m² basis with an approximate 2-fold safety

margin [NOAEL in rat (30 mg/kg) x 6 (to convert dose in mg/kg to dose in mg/m²) = 180 mg/m² vs human 200 mg daily dose = 2.9 mg/kg x 37 (dose in mg/kg to dose in mg/m²) which converts to 108 mg/m² for a 70 kg person].

The safety of antroquinonol in patients with mild to moderate pneumonia caused by COVID-19 will be confirmed at 100 mg BID in the sentinel and expansion cohorts, which is within the animal efficacy range.

Treatment duration was selected based on the clinical presentation of the disease. Patients with COVID-19 experience systemic symptoms for approximately 7 to 10 days, and patients with disease progression but without ventilator use are typically hospitalized for 5 to 7 days. In a subset of patients, a cytokine storm can emerge resulting in complications. A treatment duration of 14 days should be adequate to treat the infection and prevent the immune response complications.

4. SELECTION OF STUDY POPULATION

Prospective approval of protocol deviations to recruitment and enrollment criteria, also known as protocol waivers or exemptions, is not permitted.

4.1. Inclusion Criteria

Patients must satisfy all of the following criteria at the screening visit unless otherwise stated:

1. Willing and able to provide informed consent.
2. Male or female patients between 18 and 80 years of age.
3. Oxygen saturation <94% in room air at screening.
4. Hospitalized with mild COVID-19 disease (not requiring oxygen therapy [WHO COVID-19 Clinical Improvement Ordinal Scale, score of 3] or requiring oxygen therapy by mask or nasal prong [WHO COVID-19 Clinical Improvement Ordinal Scale, score of 4]). Requirement of oxygen therapy by mask with reservoir to treat severe COVID-19 pneumonia is not allowed for enrollment.
Note: Hospitalized patients can also include patients admitted to centers conditioned as hospitals to treat COVID-19 patients.
5. Chest x-ray or CT scan consistent with pneumonia.
6. Onset of COVID-19 symptoms within 2 weeks prior to randomization.
7. SARS-CoV-2 infection confirmed by a PCR test, antigen, or any authorized commercial or public health assay (nasopharyngeal, oropharyngeal, or respiratory samples, not serology testing).
8. Male patients and female patients of childbearing potential must agree to use protocol-specified methods of contraception ([Appendix 4](#)).
9. Female patients of childbearing potential must have a negative pregnancy test at screening or pretreatment on Day 1.
10. Male patients must agree not to donate sperm from the first dose through 90 days after the last dose of study treatment; female patients of childbearing potential should refrain from donation of ova from Day 1 until 90 days after the last dose of study treatment.
11. Patient is, in the opinion of the investigator, willing and able to comply with the study treatment regimen and all other study requirements.

4.2. Exclusion Criteria

Patients will be excluded from the study if they satisfy any of the following criteria at the screening visit unless otherwise stated:

1. Female patient is pregnant or breastfeeding.
2. Any patient's concomitant life-threatening condition, including but not limited to: requiring mechanical ventilation, acute respiratory distress syndrome, shock, or cardiac failure.
3. Evidence of multi-lober consolidation pneumonia or cavities on chest x-ray or CT scan.
4. Severe COVID-19 disease as defined by the WHO COVID-19 Clinical Improvement Ordinal Scale, scores of 5 (non-invasive ventilation or high-flow oxygen), 6 (intubation and mechanical ventilation), or 7 (ventilation + additional organ support-pressors, renal replacement therapy, ECMO).
5. Medical history significant for the following pulmonary diseases: lung cancer, cystic fibrosis, empyema.
6. Respiratory rate >30 respirations per minute.
7. History of abuse of drugs or alcohol that could interfere with adherence to study requirements as judged by the investigator.
8. Treatment with other drugs thought to possibly have activity against COVID-19 within 7 days prior to enrollment or concurrently. Note: remdesivir or other authorized treatments for COVID-19 is allowed if considered SoC, if started prior to randomization or during the study.
9. Use of *A. camphorata*-containing products within 2 weeks prior to the first administration of study drug.
10. Use of other investigational drugs within 30 days of dosing, or plans to enroll in another clinical trial of an investigational agent while participating in the present study.
Note: authorized COVID-19 vaccines are not considered investigational and are not exclusionary.
11. Clinically significant abnormal ECG at screening, as determined by the investigator.
12. Patient requires frequent or prolonged use of systemic corticosteroids (≥ 20 mg of prednisone/day or equivalent for >4 weeks) or other immunosuppressive drugs (eg, for organ transplantation or autoimmune conditions).
13. Abnormal laboratory values at screening:
 - a. Estimated glomerular filtration rate <50 mL/min.
 - b. Alanine aminotransferase (ALT) or aspartate aminotransferase (AST) $>5 \times$ upper limit of normal (ULN), or ALT/AST $>3 \times$ ULN plus total bilirubin $>2 \times$ ULN.
 - c. Total bilirubin $>1.5 \times$ ULN, unless the patient has known Gilbert's syndrome.
 - d. Hemoglobin <9 g/dL for females or <11 g/dL for males.

- e. Absolute neutrophil count <1,500/mm³.
- f. Thrombocytopenia (platelets count <100 × 10⁹/L).

14. Treatment with any antiviral drugs (except remdesivir or other authorized treatments for COVID-19), or with any drugs known to be strong inducers or inhibitors of CYP2C19, CYP3A4, CYP2C8, and CYP2E1 within 14 days or 5 half-lives prior to the start of study treatment. Drugs with a narrow therapeutic index that are substrates of 1A2, 2B6, 2C8, 2C9, 2C19, 3A, and 2D6 are also prohibited.

15. Inability to swallow oral medications or a gastrointestinal disorder with diarrhea (eg, Crohn's disease), malabsorption, or diarrhea of any etiology at baseline.

16. Any other clinically significant medical condition or laboratory abnormality that, in the opinion of the investigator, would jeopardize the safety of the patient or potentially impact patient compliance or the safety/efficacy observations in the study.

4.3. Disease Diagnostic Criteria

Patients with SARS-CoV-2 infection confirmed by a PCR test, antigen, or any authorized commercial or public health assay (nasopharyngeal, oropharyngeal, or respiratory samples, not serology testing) and any symptoms of mild to moderate COVID-19 as defined by the WHO Clinical Improvement Ordinal Scale are required for enrollment (see [Section 4.1](#)).

4.4. Discontinuation Criteria

4.4.1. Screen failures

[figure not shown]
Screen failures are defined as patients who consent to participate in the clinical study but are not subsequently enrolled in the study. A minimal set of screen failure information is required to ensure transparent reporting of screen failure patients to meet the Consolidated Standards of Reporting Trials publishing requirements and to respond to queries from regulatory authorities. Minimal information includes demography, screen failure details, eligibility criteria, and any SAEs.

Patients who do not meet the criteria for participation in this study may not be rescreened.

4.4.2. Hepatic injury or renal impairment

4.4.2.1. *Hepatic injury*

Discontinuation of study treatment for abnormal liver tests should be considered by the investigator when a patient meets one of the conditions outlined in [Figure 2](#) or if the investigator believes that it is in the best interest of the patient.

Figure 2: Stopping Criteria for Liver Injury

Abbreviations: ALT = alanine aminotransferase; INR = international normalized ratio; ULN = upper limit of normal
 Note: INR value is not applicable to patients on anticoagulants.

4.4.2.2. *Renal impairment*

If a patient has renal impairment (creatinine clearance <50 mL/min), treatment should be discontinued.

4.4.3. **Discontinuation of study treatment**

A patient may be discontinued early from study drug treatment (ET of study treatment) for the following reasons:

- Lack of efficacy (e.g. patients who require nonstudy antiviral or anticytokine therapy due to progression of COVID-19), and the investigator's decision. Note: remdesivir or other authorized treatments for COVID-19 is allowed if considered SoC, if started prior to randomization or during the study. Initiation of remdesivir or other authorized treatments for COVID-19 during the study will be considered a treatment failure if started due to progression of disease.
- Adverse event
- Withdrawal by patient (specify reason in the eCRF)
- Lost to follow-up
- Death

- Physician decision (i.e. investigator decision based on protocol deviation, assessment that it is not in the patient's best interest to continue, or other reason [specify reason in the eCRF]).
- Sponsor decision (specify reason in the electronic case report form [eCRF])

No temporary treatment discontinuation is permitted.

Patients who discontinue study treatment prematurely will be asked about the reason(s) for discontinuation and will be asked to continue all assessments up to Day 28. Patients will be educated about the continued scientific importance of their data and encouraged to complete the Day 28 Follow-up/EOS assessments even if they discontinue study treatment prematurely.

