1.3. Benefit-risk Assessment

There remains a significant unmet medical need for treatment options for patients with mild to moderate pneumonia due to COVID-19. Antroquinonol has been observed as a drug with a relatively low-toxicity profile in preclinical pharmacology and toxicology studies and clinical studies. To date, no fatal or severe/serious ADRs have occurred in the clinical studies of antroquinonol. Based on previous studies, antroquinonol has no hepatotoxicity and no cardiac toxicities. Safety of antroquinonol has not been assessed in a patient population hospitalized with mild to moderate pneumonia due to COVID-19. More detailed information about the known and expected benefits and risks and reasonably expected AEs of antroquinonol in other patient populations may be found in the current IB.⁵

The results of PK studies, including absolute bioavailability determination, organ distribution, metabolism related to cytochrome P450 isoform (CYP450), main metabolites in rat urine, and cross-species metabolite comparisons indicated fast absorption, substantial organ distribution (especially in lung, heart, and kidney), and CYP450-involved metabolism profiles of antroquinonol.

No other proven therapeutic options exist for the patient population hospitalized with mild to moderate pneumonia due to COVID-19. If proved effective, use of antroquinonol in mild to moderate pneumonia due to COVID-19 would fulfil an urgent unmet medical need in the context of a global pandemic and a novel coronavirus.

As the design of this study is considered conservative and acceptable, and the study subjects targeted are patients with limited treatment options, the overall benefit/risk assessment supports further investigation of antroquinonol in hospitalized patients with mild to moderate pneumonia due to COVID-19 in a Phase 2 setting.

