5.4. Dose Modification

No modification of study treatment dosage for patient management will be permitted.

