7.2.3. Clinical laboratory evaluations

Blood and urine samples will be collected for clinical laboratory evaluations at the times indicated in the Schedule of Assessments in [Appendix 5](#). Clinical laboratory evaluations are listed in [Appendix 2](#). Additional clinical laboratory evaluations will be performed at other times

if judged to be clinically appropriate or if the ongoing review of the data suggests a more detailed assessment of clinical laboratory safety evaluations is required.

Serum pregnancy test is to be performed in female patients of child bearing potential at a local (site) laboratory, during screening or Day 1, discharge, and ET/EOT. A urine pregnancy test may be performed but must be confirmed with a serum pregnancy test (screening only). The Follow-up/EOS visit test will be a urine pregnancy test only (no serum pregnancy test confirmation). Additionally, local/country regulations will be followed as applicable (eg., a pregnancy test one month following the last dose of study treatment in female patients of childbearing potential).

Screening laboratory test will be assessed by a local laboratory, and baseline and postbaseline laboratory tests will be assessed by a central laboratory. If delays in transportation of the samples are encountered, then local safety laboratory samples can be obtained instead for samples that can't be frozen for shipment (e.g. hematology and urine). Baseline laboratory tests can be done once patients eligibility is confirmed. The investigator will perform a clinical assessment of all clinical laboratory data.

All screening laboratory results must be available and reviewed before the patient receives the first dose of study treatment on Day 1. After the test results are evaluated, the investigator should judge whether the patient is still eligible to stay in the study. Significant abnormal values occurring during the study will be followed until repeat test results return to normal, stabilize, or are no longer clinically significant.

In this study, clinical laboratory tests will be performed predose on Days 1, 5, and 14 (+2 days).

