Appendix 2. Clinical Laboratory Evaluations

The following clinical laboratory analytes will be assessed:

Table 2: Clinical Laboratory Evaluations

Clinical Chemistry:	Hematology (complete blood count):
Albumin	Hematocrit
ALP	Hemoglobin
ALT	MCH
AST	MCHC
BUN	MCV
Calcium	Platelet count
Chloride	Red blood cell (RBC) count
Cholesterol	White blood cell (WBC) count
Creatinine	WBC differential
GGT	(% and absolute values):
Glucose	Basophils
eGFR	Eosinophils
LDH	Lymphocytes
Phosphorus	Monocytes
Potassium	Neutrophils
Sodium	
Total Bilirubin	
Total CO ₂ (measured as bicarbonate)	For female patients of child bearing potential:
Total Protein	Pregnancy test (urine, serum)
Triglycerides	
Uric acid	
Complete Urinalysis:	
Color and appearance	
pH and specific gravity	
Bilirubin	
Glucose	
Ketones	
Leukocytes	
Nitrite	
Occult blood	
Protein	
Microscopic (including RBCs and WBCs)	

Abbreviations: ALP = alkaline phosphatase; ALT = alanine aminotransferase; AST = aspartate aminotransferase; BUN = blood urea nitrogen; CBC = complete blood count; CO₂ = carbon dioxide; eGFR = estimated glomerular filtration rate; GGT = gamma glutamyl transferase; LDH = lactate dehydrogenase; MCH = mean corpuscular hemoglobin; MCHC = mean corpuscular hemoglobin concentration; MCV = mean corpuscular volume; RBC = red blood cell; WBC = white blood cell.

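### Entry screens on eGFR below 50 mL/min but treatment stops permanently at creatinine clearance below 50 mL/min, so some older, light patients may be enrolled already meeting the stop rule

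*Protocol*

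**What the plan says.** Exclusion 13a (Protocol Section 4.2, repeated in the synopsis) excludes a patient with "Estimated glomerular filtration rate <50 mL/min". The renal stop in Section 4.4.2.2 reads: "If a patient has renal impairment (creatinine clearance <50 mL/min), treatment should be discontinued". It describes a state and requires no fall from baseline.

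Two other rules make the stop final. Section 4.4.3 says "No temporary treatment discontinuation is permitted", and Section 5.4 says "No modification of study treatment dosage for patient management will be permitted".

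The laboratory panels in Protocol Appendix 2 (Table 2) and SAP Section 7.7.3 list creatinine and eGFR. Neither lists creatinine clearance. No section gives an equation or a collection method for either measure. Height and weight are measured at screening only (Appendix 5, footnote e). Enrolment runs from 18 to 80 years with no weight limit (Section 4.1).

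**The concern.** Two measures share one number and one unit but are not the same quantity. A calculated clearance normally uses body weight; the usual eGFR equations do not. They can fall on opposite sides of 50 mL/min in the same patient on the same blood sample, mostly in people who are old and light.

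Two things follow. A patient could be randomized in line with 13a while already meeting a rule that ends treatment for good. And two sites could treat the same patient differently, one stopping on a hand-calculated clearance and the other continuing on the eGFR from the panel, with both able to claim compliance. What is at stake is who receives study drug, who is taken off it, and whether sites act alike.

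**Working it through.** The plan states no figure to reproduce. The check is whether a single creatinine value can pass 13a and meet 4.4.2.2.

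**Inputs from the documents.** Both cut-offs are 50 mL/min (Sections 4.2 and 4.4.2.2). The upper age limit is 80 (Section 4.1). The only body weight the protocol uses is 70 kg (Section 3.4).

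**Assumptions, because the documents give none.** Cr is in mg/dL. Other weights, and all heights, are chosen for illustration.
- Clearance (Cockcroft-Gault) = (140 − age) × kg / (72 × Cr), × 0.85 if female.
- CKD-EPI 2021 = 142 × (Cr/κ)^−1.2 × 0.9938^age, × 1.012 if female. κ is 0.7 for women and 0.9 for men. This is the form for Cr above κ, which covers every case below.
- CKD-EPI 2009 = 141 × (Cr/κ)^−1.209 × 0.993^age, × 1.018 if female.
- MDRD = 175 × Cr^−1.154 × age^−0.203, × 0.742 if female.
- These three give mL/min per 1.73 m2 (indexed). Rule 13a is written in plain mL/min, so I also de-index: eGFR × BSA/1.73, with BSA = √(kg × cm/3600).

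**One patient in full: woman, 78 years, 55 kg, Cr 0.9.**
- CKD-EPI 2021: 142 × (0.9/0.7)^−1.2 × 0.9938^78 × 1.012 = 65.4
- CKD-EPI 2009: 141 × (0.9/0.7)^−1.209 × 0.993^78 × 1.018 = 61.2
- MDRD: 175 × 0.9^−1.154 × 78^−0.203 × 0.742 = 60.6
- De-indexed at 150 cm (BSA 1.514): 57.3, 53.6, 53.0. At 165 cm (BSA 1.588): 60.1, 56.2, 55.6.
- Clearance: 62 × 55 × 0.85 / (72 × 0.9) = 44.7

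She is eligible under every eGFR version and meets the stop rule before her first dose.

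**Creatinine bands that pass entry and meet the stop rule** (to 0.01 mg/dL; order CKD-EPI 2021 / CKD-EPI 2009 / MDRD):

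| Patient | Clearance = 50 at Cr | Band, indexed eGFR | Band, de-indexed eGFR |
|---|---|---|---|
| Woman 78 y, 55 kg, 160 cm | 0.805 | 0.81–1.12 / 0.81–1.06 / 0.81–1.06 | 0.81–1.03 / 0.81–0.97 / 0.81–0.97 |
| Man 75 y, 70 kg, 170 cm | 1.264 | 1.27–1.45 / 1.27–1.37 / 1.27–1.38 | 1.27–1.51 / 1.27–1.42 / 1.27–1.44 |
| Woman 75 y, 70 kg, 160 cm | 1.074 | 1.08–1.14 / 1.08 only / none | 1.08–1.16 / 1.08–1.10 / 1.08 only |
| Man 80 y, 90 kg, 175 cm | 1.500 | none / none / none | 1.51–1.66 / 1.51–1.55 / 1.51–1.61 |
| Man 60 y, 90 kg, 175 cm | 2.000 | none / none / none | none / none / none |

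**First age with any overlap at 70 kg** (same order):
- Men, 170 cm: 59 / 66 / 69 indexed; 53 / 61 / 64 de-indexed.
- Women, 160 cm: 70 / 75 / 76 indexed; 67 / 73 / 75 de-indexed.

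**The other boundary.** If one equation is used for both rules, the two conditions are complements at 50 mL/min and no creatinine value satisfies both. The overlap is then zero.

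**The case against.** The strongest reply is that the overlap comes from pairing equations that the documents never name. Both rules use 50 and plain mL/min, which suggests that one threshold may have been meant, and a site that uses one calculated value for both has no conflict. This stands as a limit on the finding. It does not settle the matter, because nothing in the text tells sites to do that, and the panel reports eGFR while the stop rule asks for something else.

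A reader might infer that the stop rule cannot be applied because clearance is not on the laboratory lists. The documents do not support that: creatinine is on both lists and weight is taken at screening, so clearance can be calculated. The rule is unspecified, not unusable.

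Investigators also have two routes to keep such a patient out. Exclusion 16 covers "Any other clinically significant medical condition or laboratory abnormality that, in the opinion of the investigator, would jeopardize the safety of the patient", and after the screening results Section 7.2.3 says "the investigator should judge whether the patient is still eligible to stay in the study". Both depend on judgment, and both help only if the site calculates clearance at screening, which nothing requires.

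A stricter measure on treatment may be deliberate. The dose is fixed, and Section 1.3 names the kidney among the organs to which the drug distributes. The protocol gives no reason for the renal rule, however, and if clearance below 50 mL/min is a reason not to continue, it is hard to see why it is not a reason not to start.

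Finally, there are few occasions to trigger the stop. Section 7.2.3 schedules laboratory tests on Days 1, 5 and 14, the schedule of assessments adds discharge, and Day 14 is already the end of treatment. This limits the practical effect and is one reason to rate the point as minor.

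**Conclusion.** The two rules conflict as written: the entry rule can admit a patient who already meets a permanent stop. For older, light patients this holds under all three eGFR equations, indexed or not, provided clearance is by Cockcroft-Gault. At 70 to 90 kg it is less certain. At 70 kg the overlap starts somewhere between ages 53 and 69 in men and 67 and 76 in women, and for a 90 kg, 80-year-old man it appears only with de-indexed eGFR. It should therefore not be described as a general feature of older patients whatever their weight.

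The documents give no joint distribution of age, weight and creatinine, so the number affected cannot be calculated. It is probably small.

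A reader might also infer that the trial's main result is threatened. It is not. The primary analysis set is ITT (Protocol Section 8.2), and patients who stop treatment are asked to continue assessments to Day 28 (Section 4.4.3). Neither renal rule is among the per-protocol exclusions in SAP Section 5.4.1. No power, alpha or endpoint figure is involved. The effect is on dosing and on consistency between sites.

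**What to change.** Keep the stop rule in Section 4.4.2.2 as it is and name its equation, for example Cockcroft-Gault with screening weight. Apply the same creatinine clearance threshold of 50 mL/min in exclusion 13a, calculated from the screening creatinine, and make the matching change in the synopsis. On the same creatinine value, nobody could then be enrolled who already meets the stop rule.

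It is safer to add clearance to 13a than to substitute it for eGFR, because substitution could admit some heavier patients who are now excluded. For an 80-year-old, 90 kg man with creatinine 1.45, clearance is 60 × 90 / (72 × 1.45) = 51.7, while indexed CKD-EPI 2021 is 142 × (1.45/0.9)^−1.2 × 0.9938^80 = 48.7. If eGFR stays, its equation and indexing should be named too.

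The cost is a sentence in each section. Creatinine and weight are already collected, so no new sample, visit or SAP analysis is needed. The downside is that a few older, light patients who now qualify would be excluded.

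The alternative, moving the stop rule to eGFR, also removes the overlap but relaxes a safety stop, and should be left to the clinical team. For the 78-year-old, 55 kg woman, clearance is 62 × 55 × 0.85 / (72 × Cr) = 2898.5 / (72 × Cr). Her eGFR reaches 50 at Cr 1.126, 1.064 or 1.062 indexed, and at 1.035, 0.979 or 0.973 de-indexed at 160 cm. She would stop only when clearance had fallen to about 36 to 41 mL/min.
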